8.6.3 Analysis of Quality of Life Questionnaire (FACT-hep)

8.6.3.1 Analysis of FACT-hep Scores

The total, domain, and individual question scores of the FACT-hep QoL instrument and their differences from baseline will be summarized at each time point by treatment group. The two treatment groups will be compared by applying a mixed linear model repeated measures analysis using a residual maximum likelihood estimation with the treatment, visit and the interaction between treatment and visit as factors, and the baseline score as a covariate. If the interaction term has a 2-sided p-value ≥ 0.15 then the model will be refitted without the interaction term. The Kenward-Roger approximation will be used to estimate the degrees of freedom. An unstructured covariance approach will be applied. If the fit of the unstructured covariance structure fails to converge, the following covariance structures will be tried in order until convergence is reached: Toeplitz with heterogeneity, autoregressive with heterogeneity, Toeplitz, and autoregressive. Means and least squares mean difference between treatment groups, along with a two-sided 95% CI and p-value for the difference between treatments will also be provided. This analysis will be performed on the mITT and PP populations.

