	
allowing the study to be stopped early for efficacy. A second interim analysis is planned at approximately, but no less than, 250 deaths, with a two-sided p-value ≤ 0.0151 allowing the study to be stopped early for efficacy.
 
A conditional power of less than or equal to 15% at each of the interim analyses will result in the study stopping early for futility.
 
Sample size modification will be considered at the second interim analysis following the approach described in Mehta & Pocock (2011)¹⁶ which employs an un-weighted test statistic at the final analysis as recommended by Burman & Sonneson (2006)¹⁷.
 
Final Analysis of primary endpoint: The final analysis, without a sample size modification, will be performed when approximately, but no less than, 417 deaths have occurred. A two-sided p-value ≤ 0.0363 is required to declare a statistically significant improvement in median OS at the final analysis.
 
If the sample size is increased after the second interim analysis, the final analysis will be performed when approximately, but no less than, 564 deaths have occurred, which will result in 80% power to detect an improvement in median OS from 10.7 to 13.7 months using a log rank test with a final two-sided alpha of 0.0363.
 
Analysis of secondary efficacy endpoints
 
Comparison between treatment groups for all secondary endpoints will be conducted at the final analysis with a two-sided alpha of 0.05.
 
Time to event endpoints (ie, TTP, TTUP, TTSP) will be compared between treatment arms using a log-rank test. Tumor response rates will be compared between treatment arms using the continuity adjusted Newcombe-Wilson test. The FACT-Hep score will be compared between treatment arms using a mixed linear model with baseline score and the relative time from baseline as covariates.
 
Safety Analysis: All patients who received study treatments at least once will be included in the safety analysis. All Adverse events (AEs) will be reported according to the National Cancer Institute Common Terminology Criteria for Adverse Events v 4.0 (CTCAE) grades and coded using the Medical Dictionary for Regulatory Activities (MedDRA). The incidence of treatment emergent adverse events (events which were not present at baseline or worsened in severity following the start of treatment) will be summarized according to MedDRA primary system-organ class (SOC) and preferred term (PT). Laboratory values will be summarized by treatment group over time and overall.
 
A feasibility safety assessment will be conducted after the first 20 patients in the treatment group have received both TS and sorafenib therapy.
 
Poolability and Other Analysis: Multivariate Cox regression analysis of time-to-event efficacy endpoints will be conducted on stratification criteria and other factors such as age, gender, duration of disease prior to randomization.
 
As a sensitivity analysis, to address the poolability of data across regions, study sites and gender, a Cox regression analysis of the primary efficacy endpoint, OS, will be conducted with factors of region, study site and gender, and to determine the impact of these factors on OS. Note: region and study site will not be included simultaneously in the model due to collinearity.
 
Should the impact of region, site or gender on OS be statistically and clinically relevant, the reasons for the observed differential treatment effect, such as patient

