- Quality of Life. The total score of FACT-Hep will be calculated, the scores of each domain and each question at each time-point and their differences from baseline will be summarized for each treatment group. The two treatment groups will be compared applying a mixed model repeated measures analysis with the treatment, visit and the interaction between treatment as factors, the baseline score as a covariate and further adjusted for the interaction between baseline and visit. A deterioration in QOL is defined as a 7-point decline in the total score or death whichever occurs first. The time to deterioration in QOL (TTDQoL) will be calculated as the interval between the randomization date and deterioration in QOL. The Kaplan-Meier method will be used to estimate the TTDQoL curves in the two treatment arms; comparison between the curves will be performed using the log-rank test

A detailed description of data censoring handling for patients will be defined in the Statistical Analysis Plan.

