6.2.2 Windows

For the purpose of statistical analysis, time windows will need defining for presentations that summarize values by visit. The windows for the visits following baseline will be constructed in such a way that the upper limit of the interval falls half way between the two visits (the lower limit of the first post-baseline visit will be Day 2), as shown below. The assignment of data to visit windows will use the relative day defined in Section 6.2.1.1.

Table 3 Analysis Windows for Assessments Performed at Eight Week Intervals

Week	Scheduled Day	Visit Window for Analysis (Days)
Week 8	57	2 – 85
Week 16	113	86 – 141
Week 24	169	142 – 197
...		
End of Study		Latest assessment available*

*Last assessment should be assigned to a Week X based on the visit windows as well as to the end of study evaluation.

If a patient has more than 1 assessment occurring in the same visit window, the data from the assessment closest to the scheduled day will be used. If 2 assessments have the same distance from the scheduled day, the data of the assessment after the scheduled day will be used. Note that the visit windows will not be used for time-to-event endpoints and subject-level tumor response endpoints (i.e. objective response rate and disease control rate).

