8.6.2 Analysis of Secondary Efficacy Variables

For secondary efficacy endpoints, each comparison between treatment groups will be conducted at $\alpha=0.05$ (two-sided). Secondary study endpoints will be analyzed only at the final analysis to determine the statistical significance, if any, between the treatment groups. Study-wise Type I error will be controlled using a sequential hierarchical approach, as shown in the figure below. That is, if the primary comparison is statistically significant, the secondary endpoints will be analyzed as secondary endpoints in order of the list below and will continue as long as the obtained 2-sided probability is equal to or less than 0.05. If a probability of greater than 0.05 is obtained, the inferential analysis of secondary endpoints will stop and not proceed further down the ordered list. In this manner the overall study alpha is protected and no further adjustment for multiplicity of analyses is required. If a probability of greater than 0.05 is obtained for an endpoint then the analysis of that endpoint and the endpoints further down the ordered list will still be presented but will be considered as exploratory endpoints rather than secondary endpoints.

Hierarchical approach to control study-wise Type I error of primary and secondary efficacy endpoints

^a Type I error is controlled at $\alpha=0.05$ (two-sided) over the 2 planned interim analyses and final analysis.

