11.2 APPENDIX 2: STATISTICAL ANALYSIS AND PROGRAMMING DETAILS

The SAS procedure LIFETEST will be used in the Kaplan-Meier analyses. Patients who did not have an event will be censored.

The following code will be used:

```
proc lifetest data=all method=km alpha=0.05 outsurv=interval;  
    time aval*censr(1);  
    strata trtp;  
    id usbjid;  
run;
```

The SAS procedure PHREG will be used in the Cox regression analysis of time-to-event endpoints. Patients who did not have an event will be censored. The SAS method of discrete will be used to handle ties.

The SAS procedure MIXED will be used for mixed modeling. The following code will be used:

```
proc mixed method = reml;  
class BASE TRT VISIT SUBJID;  
model CH= BASE TRT VISIT TRT*VISIT /s ddfm=kr;  
repeated VISIT/type=UN subject=SUBJID;  
lsmeans TRT*VISIT /slice=VISIT diff alpha=0.05 cl;  
run;
```

where BASE is the baseline score, TRT is the assigned treatment, VISIT is the visit based on the window mapping, CH is the change from baseline.

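### The SAP lets a 0.15 pre-test choose the FACT-Hep model and names no single QoL contrast, so the 5% level for this test cannot be shown to hold

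*SAP*

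**What the plan says.** The documents describe three models for the FACT-Hep score.

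- **Protocol 10.2.3.2:** a repeated-measures mixed model with treatment, visit, their interaction and baseline, "further adjusted for the interaction between baseline and visit". There is no pre-test.
- **Protocol synopsis:** a "mixed linear model with baseline score and the relative time from baseline as covariates". It has no baseline-by-visit term.
- **SAP 8.6.3.1 and the Appendix 2 code:** treatment, visit, treatment-by-visit and baseline, without baseline-by-visit. The text adds that, when the two-sided p-value for the interaction is 0.15 or more, "then the model will be refitted without the interaction term".

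SAP 8.6.3.1 then promises a least-squares mean difference with a confidence interval and a p-value for the treatment comparison. It names no visit or averaging rule. It lists total, domain and single-question scores without saying which one decides. The only contrast statement printed in Appendix 2 is an LSMEANS line on TRT*VISIT, sliced by visit.

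QoL is a listed secondary endpoint (SAP 6.4.2). Under SAP 8.6.2, "if the primary comparison is statistically significant, the secondary endpoints will be analyzed as secondary endpoints in order of the list below", and testing "will continue as long as the obtained 2-sided probability is equal to or less than 0.05".

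**The concern.** A test in a fixed sequence needs one p-value defined in advance. Here the interaction p-value decides which model is reported. If the interaction is removed, there is one overall treatment difference. If it is kept, the printed code returns as many differences as there are visits. The plan does not say which of them answers the QoL question.

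If a reader could pick a favourable visit in that branch, the nominal 5% would not hold, and the step from QoL to any later endpoint in the sequence would rest on it. The change from the protocol model also means that the pre-specified analysis differs from the protocol with no reason given. SAP 5.2.2 does declare comparable changes for TTP and for the response-rate test.

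**Working it through.** **Plan's own figure.** The 0.05 is a set level, so there is nothing to derive. As a benchmark, one fixed overall contrast with no pre-test rejects in 4.97 to 5.04% of null trials across 24 simulated scenarios (1,000,000 draws each).

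**Inputs from the documents.** Secondary level 0.05 two-sided (SAP 8.6.2); interaction threshold 0.15 (SAP 8.6.3.1); 1:1 allocation (protocol 9.2.14); effective size 468, so 234 per arm (SAP Appendix 5); QoL every 8 weeks until death, with no cap on visits (protocol 9.2.13).

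**Assumed, because the documents give no figures.** 3, 6 or 9 visits; compound-symmetric (CS) or AR(1) correlation of 0.5 or 0.7; retention of 100% or 80% from one visit to the next.

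**Method.** Visit-wise treatment differences are drawn under the null and the interaction is tested at 0.15. If it is removed, the common treatment effect is tested. If it is kept, one of the candidate rules below is applied.

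**Formula.** The interaction is kept in 15% of null trials. The common-effect estimate is independent of the interaction contrasts, so the removed branch keeps its 5%. Hence

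type I error = 0.85 × 0.05 + 0.15 × c = 0.0425 + 0.15c,

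where c is the chance of rejection given that the interaction was kept.

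| Rule when the interaction is kept | Type I error over 24 scenarios |
|---|---|
| Any visit at p≤0.05 | 7.8 to 16.1% |
| Any visit, Bonferroni | 5.3 to 7.3% |
| One named visit (first or last) | 5.3 to 6.9% |
| Equal-weight average over visits | 5.0 to 5.5% |

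Numbers put into the formula:

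- Any visit, lowest (3 visits, CS 0.7, full retention): c = 0.239; 0.0425 + 0.15 × 0.239 = 0.078.
- Any visit, highest (9 visits, AR(1) 0.5, 80% retention): c = 0.791; 0.0425 + 0.15 × 0.791 = 0.161.
- Last visit, highest (3 visits, AR(1) 0.5, 80% retention): c = 0.172; 0.0425 + 0.15 × 0.172 = 0.068 (simulated 0.0685).
- Average, highest (9 visits, AR(1) 0.5, 80% retention): c = 0.0803; 0.0425 + 0.15 × 0.0803 = 0.0545.

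A separate null simulation gave 7.0 to 15.8% for any visit, 5.4 to 6.6% for the last visit and 4.9 to 5.5% for the average. Hence the rounded 7 to 16% for any visit.

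**Baseline-by-visit alone.** With 6 visits, slopes that vary by visit and 1,500 runs (standard error about 0.6 points), the rejection rate was 5.5% without the term and 5.5% with it when dropout was the same in both arms. In an assumed case where dropout differed by arm and depended on baseline, it was 7.9% without and 6.0% with.

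**The case against.** **No any-visit rule is stated.** This is the strongest defence. SAP 8.6.3.1 speaks of one p-value. Because TRT is in the model, PROC MIXED's default output also includes an overall treatment test that averages over visits, which is close to the benign row of the table. This stands against any claim that the test exceeds 5% outright. It does not supply the missing rule: a default output table is not a named decision test, and the only contrast the SAP prints is per visit.

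**The gated test may be something else.** The hierarchy figure is not visible. SAP 8.6.5 counts time to deterioration in QoL (TTDQoL) among the secondary time-to-event endpoints, and SAP 8.6.3.2 gives it its own 0.05 level. The mixed model may therefore not be the gated test. That limits the consequence and is a further reason to name the test. The OS gate also protects study-wise error when OS has no effect; the issue arises once OS and any earlier endpoints are significant.

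**Undeclared, as far as can be read.** SAP 5.2.4 and part of the version history are not visible, so the statement covers the visible text only. The synopsis also lacks baseline-by-visit, so the protocol is itself inconsistent.

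**A duplicated last score.** A reader might infer that each patient's final score enters the model twice. Appendix 2 says "VISIT is the visit based on the window mapping", and the footnote to Table 3 in SAP 6.2.2 says "Last assessment should be assigned to a Week X based on the visit windows as well as to the end of study evaluation". The documents do not establish this. Those windows are introduced for by-visit summaries, and SAP 8.6.3.1 never names End of Study as a model level. The numerical evidence is thin: 400 runs, type I error of 7.8% against 5.8%, under AR(1), the last of four fallback covariance structures. It is worth one confirming sentence and is not a demonstrated error.

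**Conclusion.** The concern holds as a failure of specification. The FACT-Hep model depends on a data-driven pre-test, its deciding contrast is not named, and the SAP departs from the protocol body without saying so in the visible text. The 5% level cannot be shown to hold. Depending on a choice the SAP leaves open, type I error runs from about 5.0 to 5.5% (average over visits), through 5.3 to 6.9% (one named visit), to about 7 to 16% (any visit), against 5.0% for one fixed contrast. These figures rest on assumed visit numbers, correlations and retention.

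Two stronger readings are not supported. The first is that the QoL test does exceed 5%: that needs an any-visit rule, which the SAP does not contain. The second is that omitting baseline-by-visit inflates error by itself: with equal dropout in both arms it made no difference. The change should be made, but the primary OS analysis is not affected.

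**What to change.** 1. Delete the 0.15 refit rule.
2. Fit one fixed model with treatment, visit, treatment-by-visit, baseline and baseline-by-visit, or declare and justify dropping the last term in SAP 5.2. Bring the protocol synopsis into line.
3. Name one FACT-Hep total-score contrast as the QoL test, for example the treatment LS-mean difference averaged over a pre-specified set of visits. Make per-visit differences and the other scores descriptive.
4. State whether this test or TTDQoL is the gated one.
5. Align Appendix 2 with the text: add an LSMEANS or ESTIMATE statement for the named contrast, take BASE out of the CLASS statement because the text treats it as a covariate, and confirm that End of Study is not a VISIT level.

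The cost is SAP wording and a few lines of code. The one statistical price is slightly less precision than a main-effect model when the effect is constant over time.

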8.6.3.2 Analysis of Time to Deterioration in QoL (TTDQoL)

A deterioration in QoL is defined as a ≥ 7 -point decline in the total FACT-hep score (i.e., a change from baseline in the total score of ≤ -7 points) or death whichever occurs first. TTDQoL rates will be derived from the Kaplan-Meier estimates for each treatment group; 3, 6, 9, and 12-month TTDQoL rates will be presented, together with 95% CIs. Quartiles will be presented and 95% CIs will be calculated on the quartiles for each treatment group. A log-rank (two-sided) test will be used to compare TTDQoL between the two treatment groups at a 0.05 significance level. The HR and corresponding 95% CI will be computed from a Cox proportional hazards model. Plots of the Kaplan-Meier curves will be provided for each treatment group. This analysis will be performed on the mITT and PP populations.

TTDQoL (months) = ((Date of change from baseline in total FACT-Hep score \leq -7 or death/Censor) – Date of Randomization +1)/ 30.4375.

The censoring is performed as follows:

- If a patient does not have a baseline total FACT-hep score, then the TTDQoL time will be censored at the randomization date, regardless of whether or not TTDQoL has been observed
- If a patient received a subsequent HCC therapy before a deterioration in QoL or in the absence of a deterioration in QoL, the TTDQoL time will be censored at the last post baseline FACT-hep assessment on or before the start date of the subsequent HCC therapy where total FACT-hep score could be evaluated. If the patient has no post baseline total FACT-hep scores on or before the start date of the subsequent HCC therapy, the patient will be censored at the randomization date.
- If a patient did not have a deterioration in QoL and did not receive subsequent HCC therapy, the TTDQoL time will be censored at the last post baseline FACT-hep assessment where total FACT-hep score could be evaluated, or at the randomization date if the patient does not have any post-baseline total FACT-hep scores.
- If a patient had a deterioration in QoL immediately after two or more visits where total FACT-hep score could not be evaluated (e.g. missed visits or visits missing items to derive total FACT-hep score), the patient will be censored at the last post baseline FACT-hep assessment before the missed visits where total FACT-hep score could be evaluated. If the patient has no post baseline total FACT-hep scores before the missed visits, the patient will be censored at the randomization date.
 - Given the scheduled visit scheme of FACT-hep assessments (i.e. every 8 weeks), the definition of 2 missed visits will equate to 16 weeks since the previous FACT-hep assessment where total FACT-hep score could be evaluated, or since the randomization date if no previous post-baseline total FACT-hep scores.

8.6.4 Subgroup Analyses

Subgroup analyses of primary and secondary efficacy endpoints will be performed for the mITT population according to the subgroups listed in Section 7.7.

For each subgroup, a Cox proportional hazards model for time-to-event endpoints or a logistic regression for binary endpoints, will be fitted with treatment as the only covariate for each level of the subgroup separately.

For time-to-event endpoints, the HRs and associated 95% CIs will be summarized and presented on a forest plot, along with results of the overall analysis. If an endpoint has <10 events available at a subgroup level then the relationship between that subgroup level and endpoint will not be formally analyzed, since it is unlikely to be a meaningful analysis, and only descriptive summaries will be provided.

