4.2 Method of Assignment of Patients to Treatment Groups

Patients will be randomized to study treatment, either the Control group or the Treatment group in a 1:1 ratio.

At study enrollment, each patient will be assigned a subject identity code (e.g. T030103-001) consisting of the protocol number (T03), the country number (e.g. 01), the site number (e.g. 01), and patient number (e.g. 001).

If a patient is determined to be eligible to participate in the trial, the study site will contact the central randomization office when randomization will be determined using assignment by a computer-generated randomization scheme. Upon randomization, each patient will be assigned a 4 digits randomization number with the first digit indicating which combination of the 3 stratification factors the patient has.

A centralized randomization schedule will be generated by a statistician in the Labcorp, Biometrics department who is not associated with the conduct or analysis of the study, using a validated system. The randomization will be stratified by the following factors:

- Region (North America and Europe vs Asia)
- ECOG performance status (0 vs 1)
- Presence or absence of branch portal vein thrombosis (PVT)

In order to ensure that the study treatment groups are balanced, the schedule will have randomization numbers assigned to the 2 study treatments in blocks of 4 within each combination of the 3 stratification factors to achieve a 1:1 ratio of study treatment (i.e. an equal number of patients in each treatment group). The randomization will be performed using IVRS by Perceptive, Inc. Each eligible patient will be assigned to the next sequential randomization number within the specified stratification combination and will receive the corresponding study treatment.

Patients randomized to the Control group or the Treatment group who are unable to receive their planned study treatment will continue to be followed under the study group to which they were randomized for the purpose of the modified intent-to-treat (mITT) analysis (see Section 8.3.1).

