4.4 Determination of Sample Size

This study is an adaptive trial using a group sequential design with OS as the primary efficacy endpoint. The study is designed to detect a 3.5 months increase in median OS time, from 10.7 months in the sorafenib arm to 14.2 months in the TheraSphere arm (i.e. hazard ratio [HR]= 0.754), using a log rank test. Due to uncertainty in the expected treatment effect, a sample size re-estimation is planned, which would allow the sample size to increase in order to detect a 3.0 month increase in median OS time, from 10.7 months in sorafenib arm to 13.7 months in the TheraSphere arm (i.e. HR = 0.781).

A maximum of 417 deaths will yield 80% power to detect the target difference in median OS (i.e. HR = 0.754) with a two-sided alpha of 0.05 using a group sequential design with 2 interim analyses. It is estimated that a maximum of 520 patients will need to be recruited over 60 months, with an 18 months additional follow-up period. This includes an adjustment to take account of an assumed 5% of patients who will be lost to follow-up and for whom a date of death is not recorded, and an assumed additional 5% of patients who will erroneously be randomized because they did not meet the eligibility criteria at randomization.

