8.6.5 Assessment of Poolability

Since this is a multi-center study, analysis will be performed by pooling data across study sites. The clinical study will be conducted under a common protocol for each investigational site, except for sites in Germany, where a separate protocol was used with different eligibility criteria, mainly related to the limits on liver function tests. It is expected that approximately 1% of the total number of patients randomized in the study will be from sites in Germany.

In the event that there are small sample sizes at some sites, sites may be grouped using the following procedure to create “analysis-sites” for analysis purposes. These analysis-sites will be created for North America, Europe, and Asia independently to preserve the ability to differentiate between regions. Patients from sites in Germany will not be included in this grouping mechanism. Analysis-sites are based on a target size of at least 5 patients per treatment group at each site. If investigative sites have at least 5 mITT patients per treatment group, they will retain their identities in the analysis. All investigative sites with fewer than 5 mITT patients per treatment group will be rank ordered by size and sorted secondarily by site identification number to break ties. Starting with the smallest investigative site, patients will be combined site by site by treatment group, until the first time the resulting analysis-site has at least 5 mITT patients in each treatment group. The process continues until all investigative sites are accounted for. If the last analysis-site has fewer than 5 mITT patients per treatment group, it will be combined with the most recently created analysis-site.

To assess the poolability of data across sites, a Cox regression analysis of the primary efficacy endpoint, OS, and all secondary time-to-event endpoints (i.e., TTP, TTUP, TTSP, TTDQoL) will be conducted including factors of treatment group, analysis-site, and treatment group by analysis-site interaction. Estimates of treatment effect and 95% CIs will be calculated separately by analysis-site.

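### Apart from region and gender, the SAP plots subgroup effects level by level with no test of whether the effect differs, so an OS factor with the same true effect in both levels could easily look discordant

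*SAP*

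**What the plan says.** SAP 7.7 lists the factors for the primary and secondary efficacy endpoints. Counting both etiology categorizations there are 21, with 52 levels. Sixteen have two levels. Five have more: age group, race, Child-Pugh class, the six-category etiology and number of lesions.

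SAP 8.6.4 covers the analysis. A Cox model (time-to-event) or logistic model (binary) "will be fitted with treatment as the only covariate for each level of the subgroup separately". Levels with fewer than 10 events are only described. The display planned for the survival-type results is that "the HRs and associated 95% CIs will be summarized and presented on a forest plot", next to the overall result. No interaction term, heterogeneity test or subgroup p-value is named, and no rule is given for reading the plot. SAP 7.2 fits each covariate with treatment, also without an interaction.

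SAP 8.6.5 (poolability) goes further for three factors. Its site model is a Cox regression "including factors of treatment group, analysis-site, and treatment group by analysis-site interaction", repeated with site replaced by region and then by gender. Each interaction is judged at a two-sided 0.15 level, with follow-up if it is met. This covers OS, the secondary time-to-event endpoints and the binary endpoints, in mITT patients outside the German sites.

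**The concern.** Whether an effect differs between two kinds of patient is a question about the difference between two estimates. The 8.6.4 plot gives each estimate with its own interval and nothing on the difference. With a modest true effect and the deaths divided between levels, each level has only moderate power. One interval can then easily exclude 1 while the other does not, although nothing differs.

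The two-level factors with no interaction test anywhere in the SAP are HCC status, ECOG, branch PVT, US versus non-US, time since diagnosis, tumor replacement, extrahepatic disease, BCLC stage, alcohol etiology, prior HCC treatment, bilirubin, ALBI, AFP and maximum lesion size. Several are disease features by which readers may try to decide who benefits. The SAP does not say why gender gets an interaction test and branch PVT does not.

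**Working it through.** **Inputs**
- SAP 4.4: "A maximum of 417 deaths will yield 80% power to detect the target difference in median OS", "with a two-sided alpha of 0.05 using a group sequential design with 2 interim analyses"; medians "from 10.7 months in the sorafenib arm to 14.2 months in the TheraSphere arm", HR 0.754; smaller effect of interest, HR 0.781.
- SAP 4.2: 1:1 allocation, so log-rank information is deaths/4.
- SAP Appendix 5: looks at 188, 250 and 417 deaths, with z boundaries 2.430, 2.429 and 2.093.
- SAP 7.4: 406 deaths when version 4.0 was written; Table 8 runs from 406 to 417.
- Assumed, because the documents do not give it: the share of deaths in each level (50/50 and 30/70, with 10/90 as an extreme).
- Assumed as a further sensitivity value: HR 0.85.

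**The plan's own power first.** A trivariate normal calculation with these looks and boundaries gives 79.8% at HR 0.754 (SAP: 80%), 68.5% at HR 0.781 (SAP: 68.4%) and a one-sided type I error of 0.0250. The approximation is therefore sound for this design.

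**Power within one level.** With d deaths in the level:

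p = Φ( |ln HR| × √(d/4) − 1.96 )

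For 417 deaths split evenly, d = 208.5. At HR 0.754, |ln HR| = 0.2824 and √(208.5/4) = 7.220, so p = Φ(2.039 − 1.960) = 0.531.

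**Benefit in exactly one level.** Levels are independent with the same true HR:

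P(one only) = p1(1 − p2) + p2(1 − p1)

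- 50/50: 2 × 0.531 × 0.469 = 0.498. Both levels: 0.282. Neither: 0.220.
- 70/30 (291.9 and 125.1 deaths): p1 = 0.674, p2 = 0.352; 0.674 × 0.648 + 0.352 × 0.326 = 0.552.

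| True HR in both levels | Deaths | 50/50 | 70/30 | 90/10 |
|---|---|---|---|---|
| 0.754 | 417 | 49.8% | 55.2% | 69.8% |
| 0.754 | 406 | 49.9% | 55.1% | 69.2% |
| 0.781 | 417 | 49.0% | 52.6% | 62.7% |
| 0.85 | 417 | 33.8% | 34.7% | 37.3% |
| 1.00 | 417 | 4.9% | 4.9% | 4.9% |

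**Allowing for trial history.** SAP 7.4 says the sample size was not changed at the second look and the trial went on to a final analysis. I simulated 4 million trials with looks at 205 and 257 deaths and 410 final deaths. I assumed the planned boundaries of 2.430 and 2.429, because the boundary actually used at 257 deaths is not stated. I kept only trials with no efficacy stop and conditional power outside the promising zone. The 50/50 figure becomes 49% at HR 0.754, 42% at HR 0.781 and 24% at HR 0.85.

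**What an interaction test would do.** With identical effects it flags a split 5% of the time at 0.05, or 15% at the level used in 8.6.5. In simulation at HR 0.754 and 50/50, about 10% of splits with benefit in one level only had interaction p<0.05.

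**Its power.** For 417 deaths split evenly, the standard error of the log ratio of HRs is √(4/208.5 + 4/208.5) = 0.196. The ratio detectable with 80% power is exp[(1.960 + 0.842) × 0.196] = 1.73.

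**The case against.** The strongest reply is that the SAP never says to judge a level by whether its CI excludes 1. It gives no subgroup p-value and shows the overall estimate alongside, so a careful reader can compare each level with the overall HR. Judged instead by point estimates on opposite sides of 1, discordance at HR 0.754 occurs in only about 4% (50/50) to 18% (90/10) of trials. That stands: the figures above describe a likely misreading, not a planned inference. What remains is that the SAP offers nothing formal in its place for most factors.

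A reader might infer that the SAP has no interaction tests. It does, for site, region and gender in 8.6.5, and region and gender are also 7.7 factors.

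A reader might also infer that about half of all two-level splits will look discordant whenever the true effect is identical. The documents do not support that. The figure depends on the size of the effect, on assumed splits and on the CI reading, and it is for OS only. Event counts and effects for the secondary endpoints are not given. The factors also share patients, and BCLC stage is derived from ECOG, PVT and extrahepatic lesions. A probability per factor therefore cannot be treated as an independent count across 16 factors.

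Finally, the test is weak, and replacing the level-specific models with one joint Cox model would add an assumption of proportional baseline hazards across levels. Both are fair, and the fix allows for them.

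**Conclusion.** The gap is real and limited. Outside region and gender, 14 two-level and five multi-level factors are displayed with no test of whether the treatment effect differs. For OS at HR 0.754 with 406 to 417 deaths, a factor with no true difference has about a 50% (50/50) to 55% (30/70) chance of appearing to benefit one level only, if benefit is read as a 95% CI excluding 1. At 50/50 the chance is about 49% at HR 0.781 and 34% at HR 0.85. Allowing for the interim history barely moves the figure at the design HR and lowers it for smaller effects.

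These figures rest on the assumed splits, the log-rank normal approximation and that way of reading the plot. The primary OS test and the secondary hierarchy do not depend on these analyses. This is a low-severity reporting improvement, not a flaw in the trial's main inference.

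**What to change.** In SAP 8.6.4, keep the planned level-specific models and estimates. For every 7.7 factor, also fit one model (Cox or logistic, as the endpoint requires) with treatment, factor and treatment-by-factor interaction. For factors with more than two levels, report the overall interaction p-value, in line with the overall p-values used in SAP 7.2. State how levels with fewer than 10 events enter this model. Print the p-value on the forest plot, or in the table for binary endpoints.

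Label these p-values exploratory and unadjusted for multiplicity. With 21 factors and no true differences, about 21 × 0.05 ≈ 1 would be expected below 0.05 for each endpoint. State also that power is low (80% only for a ratio of HRs near 1.73 in an even split of 417 deaths), so a non-significant result does not show that the effect is the same.

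The cost is small. The model form is already specified for 8.6.5, and no new data are needed.
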